## 9.2.3. Vital Signs

Vital signs (body temperature, pulse/heart rate, blood pressure) will be collected at the time points indicated in the Time and Events Schedule.

## 9.2.4. Electrocardiogram

Twelve-lead ECGs will be collected at the time points listed in the Time and Events Schedule.

Only at Day 1 triplicate ECGs are required, i.e., 3 individual ECG tracings should be obtained as closely as possible in succession, but no more than 2 minutes apart. The full set of triplicates should be completed in less than 4 minutes.

During the study, the clinical investigator will review the ECG for immediate management and to mark abnormalities. A description of the overall assessment (i.e., normal or abnormal plus reason) will be made and a copy of the trace will be placed with the source data.

# 9.2.5. Physical and Neurological Examinationsa

The study investigator or other authorized and appropriately qualified designee will perform the physical examination.

Height will be measured at screening only. Body weight will be measured as per the Time and Events schedule.

The neurological examination can be adapted as necessary but should include mental status (orientation and memory); oculomotor motion and vision for cranial nerve testing; limb strength and abnormal movements for motor function; and tests of cerebellar function: gait, finger-to-nose, heel-to-shin, and rapid alternating movements. Tests of sensation (e.g., pain, vibration) should be included only if indicated by clinical history/symptoms.

<sup>a This section has been amended per Amendment INT-2.

The neurological examination will be done at screening, during the treatment phase and at the end of treatment visit (or early withdrawal visit) for all subjects. In addition neurological examinations will be completed when event driven. These events of interest include diplopia, vision impairment, gait disturbance and severe headache.

# 9.2.6. Clinical Laboratory Tests a

Blood samples (under fasted conditions whenever feasible) for serum chemistry and hematology and a random urine sample for urinalysis will be collected. The investigator must review the laboratory report, document this review, and record any clinically relevant changes occurring during the study in the adverse event section of the CRF. The laboratory reports must be filed with the source documents. The following tests will be performed a central laboratory appointed by the Sponsor:

Hematology Panel	
-hemoglobin -hematocrit - red blood cell (RBC) count - white blood cell (WBC) count with differential	
 
platelet count
 
mean corpuscular volume
 
mean corpuscular hemoglobin
 
mean corpuscular hemoglobin concentration
 

- Coagulation International normalized ratio (INR)
- -prothrombin time

-activated partial thromboplastin time (aPPT)

- Serum Chemistry Panel
  - -sodium -alkaline phosphatase -potassium -creatine phosphokinase (CPK) -chloride -lactic acid dehydrogenase (LDH) -uric acid -bicarbonate -blood urea nitrogen (BUN) -calcium -creatinine - phosphate -albumin -glucose -aspartate aminotransferase (AST) -total protein -alanine aminotransferase (ALT) -cholesterol -gamma-glutamyltransferase (GGT) -triglycerides -total and direct bilirubin -high density lipid protein -low density lipid protein

-magnesium

<sup>a This section has been amended per Amendment INT-3.

Urinalysis Dipstick Flow Cytometry -specific gravity -RBC -WBS -pH -glucose -epithelial cells -protein -blood -ketones Sediment -bilirubin -crystals -urobilinogen -casts -nitrite -bacteria -leukocyte esterase

Specific gravity, pH, glucose, protein, blood, ketones, bilirubin, and urobilinogen will be determined using a dipstick. RBC, WBC, epithelial cells, crystals, casts, and bacteria will be measured using flow cytometry. If there is discordance between the dipstick results and the flow cytometric results, the sediment will be examined microscopically.

- Urine Drug Screen: opiates (including methadone), cocaine, amphetamines, cannabinoids, barbiturates, and benzodiazepines.
- Serology (hepatitis B surface antigen (HBsAg), hepatitis C antibody (anti-HCV), HIV)
- Alcohol (blood) test

Pregnancy tests:

- In all women: serum β-HCG and urine pregnancy test will be performed at Screening and Follow-up and urine pregnancy test at study visits 2 and 9.
- In WOCBP: urine pregnancy test will be performed at all other timepoints.
- If the urine pregnancy test is positive, a serum  $\beta$ -HCG test will be performed.

The use of local laboratories is allowed in cases where initiation of treatment or safety follow-up is time-critical and the central laboratory results are not expected to be available before the need to begin dosing or if actions need to be taken for safety reasons (samples will be taken in parallel for the central laboratory).

### 9.3. Efficacy

### 9.3.1. Evaluations

The nature and content of the primary and secondary clinician administered scales as well as the Patient Reported Outcome scales are described in section 3.2. Subscales derived from the principal scales are defined below.

### Primary

Liebowitz Social Anxiety Scale (LSAS)

The LSAS was designed to assess the range of social interaction and performance situations that individuals with social phobia may fear and/or avoid (Liebowitz, 1987). The 24 items in the scale are divided into two subscales that address social interactional (11 items) and performance (13 items) situations. The clinician asks the patient to rate fear and avoidance during the past week on 0–3 Likert-type scales; however, the clinician is given latitude to question the patient's responses and adjust the ratings accordingly. Thus, the LSAS provides six subscale scores: total fear, fear of social interaction, fear of performance, total avoidance, avoidance of social interaction and avoidance of performance. An overall total score is often calculated by summing the total fear and total avoidance scores, and this index is the one most commonly employed in studies of the pharmacotherapy of social phobia (R. G. Heimberg, K. J. Horner, H. R. Juster, S. A. Safren, E. J. Brown, F. R. Schneier, M. R. Liebowitz. Psychometric properties of the Liebowitz Social Anxiety Scale. Psychological Medicine, 1999, 29, 199–212).

### Secondary

• Structured Interview Guide for the Hamilton Anxiety scale (SIGH-A)

The total and subscale scores for the SIGH-A and  $HDRS_{17}$  will be used to evaluation of efficacy on symptoms of anxiety and depression.

## • HAM- $A_6$

The HAM-A6 is a 6-item subscale derived from the original Hamilton Anxiety scale (HAM-A) (Hamilton 1959; Hamilton 1969). Because the HAM-A, like the Hamilton Depression Rating Scale (HDRS17), is a multi-dimensional scale, Bech derived a 6-item subscale, the HAM-A6, comprising five psychic anxiety symptoms: anxious mood, psychic tension, fears, intellectual disturbances, and anxious behavior observed at the interview, as well as one somatic item, muscular tension (Bech 2007), with a score range of 0 to 24. In an analysis of four pooled dose-response trials in GAD, a Mokken analysis of the HAM-A6 yielded Loevinger coefficients above 0.40 individually and combined, indicating that unlike the full HAM-A, the HAM-A6 subscale is uni-dimensional. Given a fundamental requirement for a drug to be considered to have an anxiolytic effect is that it has shown efficacy in terms of symptom reduction in the core symptoms of anxiety, and as these symptoms are captured by HAM-A6 (which is more in accordance with the DSM-5 criteria for GAD than the full HAM-A), the total HAM-A6 score is considered a sufficient statistic.

• Hamilton Depression Rating Scale (HDRS17)

A 6-item subscale from the HDRS17 (HAM-D6) will be analyzed as it has been shown to be a uni-dimensional scale that provides information to core depressive symptoms and is sensitive to treatment response (Bech 1975).

In addition the anxiety-somatization factor total score from the HDRS17 will be included (Cleary 1977). A cut-off of  $\geq$  7 on this factor has been used to define subjects with anxious depression in prior clinical trials (Fava 2008).

• Clinical Global Impression Improvement (CGI-I)

## **Patient Reported Outcome Assessments**

- Sheehan Disability Scale (SDS)
- Generalized Anxiety Disorders (GAD-7)
- Snaith-Hamilton Pleasure Scale (SHAPS)
- MOS Sleep-R
- Quality of Life Enjoyment and Satisfaction Questionnaire (Q-LES-Q)
- Self-Assessment of Treatment Experience

# 9.3.2. Endpoints

## Primary

The primary efficacy endpoint for this study will be the improvement in social anxiety symptoms, as measured by the change from baseline in the LSAS total score from baseline to the 12-week endpoint in the double-blind treatment phase.

The primary comparison will be between the JNJ-42165279 and the placebo treatment groups.

## Secondary

Secondary efficacy endpoints will include:

- The change from baseline to the 12-week endpoint for LSAS Fear/Anxiety and Avoidance subscales.
- The distribution (number and percentage) of subjects who are responders (≥50% improvement from baseline) and remitters (≥30% improvement from baseline) on the LSAS total score at the 12-week endpoint.
- The change from baseline to the 12-week endpoint for: SIGH-A total score, HAM-A6 score, HDRS17 total score, HDRS17 anxiety/somatization factor total score, HAM-D6 score and the (CGI-I) value.
- The distribution (number and percentage) of subjects who are responders (≥50% improvement from baseline) on SIGH-A total score assessed at the 12-week endpoint.

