### 4.1. Inclusion Criteriaa

Each potential subject must satisfy all of the following criteria to be enrolled in the study unless otherwise specified:

- 1. Subject must be a man or woman between 18 and 64 years of age, inclusive.
- 2. Subjects must have a primary DSM-5 diagnosis of SAD except those with performance only as a specifier. Subjects with a diagnosis of comorbid Generalized Anxiety Disorder (GAD) or Major Depressive Disorder (MDD) may be included if the investigator considers SAD to be the predominant diagnosis. Subjects with current or lifetime history of ADHD and specific phobia may be included as well.
- 3. Subjects must have a Liebowitz Social Anxiety Scale score  $\geq$  70 at screening and baseline.
- 4. Subjects with a current episode of MDD must have a HDRS17 total score  $\leq 18$
- 5. Subjects must have a body mass index (BMI=weight/height) between 18 and 35 kg/m^2, inclusive, at screening.
- 6. Criterion modified by Amendment 3.
  - 6.1. Before randomization, a **woman** must be either:
  - Not of childbearing potential: postmenopausal (>45 years of age with amenorrhea for at least 12 months, or any age with amenorrhea for at least 6 months and a serum follicle stimulating hormone (FSH) level >40 IU/L); permanently sterilized (e.g., tubal occlusion, hysterectomy, bilateral salpingectomy); or otherwise be incapable of pregnancy
  - Of childbearing potential and practicing a highly effective method of birth control consistent with local regulations regarding the use of birth control methods for subjects participating in clinical studies (i.e. one that results in a less than 1% per year failure rate when used consistently and correctly). This may include:
    - Established and ongoing use of oral hormonal methods of contraception in combination with barrier methods.
    - Established and ongoing use of patch, injected or implanted hormonal methods of contraception.
    - Placement of an IUD or IUS.

Accepted barrier methods as indicated above include:

<sup>a This section has been amended per Amendments INT-1 and 3.

- condom with spermicidal foam/gel/film/cream/suppository
- occlusive cap (diaphragm or cervical/vault caps) with spermicidal foam/gel/film/cream/suppository

Note that a barrier method on its own is not sufficient.

- Male partner sterilization (the vasectomized partner should be the sole partner for that subject).

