#### Exploratory

- The change from baseline to the 12-week endpoint for: SDS (Sheehan Disability Scale) GAD-7, Snaith-Hamilton Pleasure Scale (SHAPS) and MOS Sleep-R.
- The change from baseline to the 12-week endpoint for Quality of Life Enjoyment and Satisfaction Questionnaire (Q-LES-Q)
- Self-Assessment of Treatment Experience scale
- The change from baseline to the 12-week endpoint for: HDRS17 total score, HDRS17 anxiety/somatization factor total score and HAM-D6 score in subjects with comorbid MDD.
- The change from baseline to the 12-week endpoint for: SIGH-A total score and HAM-A6 score in subjects with comorbid GAD.
- The distribution (number and percentage) of subjects with comorbid MDD who are responders on depressive symptoms (based on two definitions: either  $\geq$ 50% or  $\geq$ 30% improvement on HDRS17 total score from baseline) at the 12-week endpoint.
- The distribution (number and percentage) of subjects with comorbid GAD who are responders on anxious symptoms (≥50% improvement on SIGH-A total score from baseline) at the 12-week endpoint.

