### 11.3. Efficacy Analysis

All efficacy analyses will be based on the intention-to-treat (ITT) analysis set. The JNJ-42165279 treatment group will be compared with placebo using the primary efficacy endpoint- change from baseline in total LSAS score during the double-blind treatment phase.

The comparison will be performed by means of a mixed-effects model using repeated measures (MMRM), with time, treatment (placebo, JNJ-42165279) and time-by-treatment interaction as factors and baseline total LSAS score as a continuous covariate and a country and presence of comorbid MDD as categorical covariates. Other covariates of interest may be included in the MMRM model. An unstructured variance-covariance matrix will be used. The treatment-placebo differences will be obtained using the appropriate contrast in the MMRM models at the 12-week endpoint.

The change from baseline for the secondary continuous efficacy endpoints will be analyzed in the same way as for the LSAS total score.

Sensitivity analyses of the primary endpoint will be performed using ANCOVA model; these will be detailed further in the Statistical Analysis Plan.

<sup>a This section has been amended per Amendment INT-3.

Descriptive statistics for values and changes from baseline (where applicable) will be provided by treatment group for all efficacy measures, including subscale scores for selected scales, at each time point of the double-blind treatment phase.

Frequency tables for remission and response of social anxiety symptoms (derived from LSAS), as well as frequency tables for response of depressive and anxiety symptoms (derived from the HDRS17 and SIGH-A) will be provided by treatment group at each time point of the double-blind treatment phase.

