5.3.1.4. LSAS $\geq 30\%$ improvement from baseline on total score

The percentage change from baseline is calculated as

$$100 * \frac{(LSAS \text{ total score at any time point} - LSAS \text{ total score at baseline})}{LSAS \text{ total score at baseline}}$$

A $\geq 30\%$ improvement on LSAS total score means that the percentage change from baseline is ≤ -30 in this calculation.

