5.3.2. Analysis Methods

For all continuous secondary endpoints, descriptive statistics of actual values and changes from baseline at each scheduled time point and endpoint will be provided by treatment group (mean, SD, median and range). This includes LSAS fear/anxiety subscale, LSAS avoidance subscale, SIGH-A total score, HAM-A₆ score, HDRS₁₇ total score, HDRS₁₇ anxiety/somatization factor score and HAM-D₆ score. A mean-SE plot over time will be presented for these continuous endpoint observed values by treatment group.

For each of the continuous secondary endpoints, the JNJ-42165279 treatment group will be compared to placebo by means of a mixed-effects model using repeated measures (MMRM) with time, treatment (placebo, JNJ-42165279) and time-by-treatment interaction as factors, baseline score of the continuous endpoint and age as a continuous covariate and country and presence of comorbid MDD as categorical covariates. An unstructured variance-covariance matrix will be used. In case of convergence problems, simpler variance-covariance structures such as Toeplitz or AR(1) will be considered. The selection of any of these structures will be determined after exploration of the observed correlation structure. The treatment-placebo differences will be obtained using the appropriate contrast in the MMRM model at the 12-week endpoint. One-sided p-values with level of significance of 20% will be derived as described in Section 5.2.2.1.

Frequency counts and percentages will be provided at each scheduled time point and endpoint by treatment group for the following variables: LSAS $\geq 50\%$ improvement, LSAS $\geq 30\%$ improvement, CGI-I, CGI-I response and SIGH-A $\geq 50\%$ improvement.

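### Does naming a ≥30% LSAS improvement remission, when response needs ≥50%, call for a change to the plan?

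*Protocol*

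**What the plan says.** Protocol section 9.3.2 sets two yes/no outcomes on the LSAS total score at week 12: "responders (≥50% improvement from baseline) and remitters (≥30% improvement from baseline) on the LSAS total score at the 12-week endpoint". Section 11.3 plans "Frequency tables for remission and response of social anxiety symptoms (derived from LSAS") by treatment group and visit. The synopsis does the same. Neither of those two places states a cut-off, and neither document gives any other definition of LSAS remission, such as an absolute score.

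Later in section 9.3.2, among the exploratory endpoints, the HDRS17 in subjects with comorbid MDD is handled differently. Subjects there are "responders on depressive symptoms (based on two definitions: either" a 50% or a 30% improvement. On that scale both cut-offs are called response.

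The SAP does not use the word remission for either LSAS variable. Table 3 and sections 5.3.1.3 and 5.3.1.4 call them ≥50% improvement and ≥30% improvement. For the lower one, the rule is that such an "improvement on LSAS total score means that the percentage change from baseline is ≤ -30 in this calculation". Section 5.3.2 then says: "Frequency counts and percentages will be provided at each scheduled time point and endpoint by treatment group for the following variables". Both LSAS variables are on the list that follows, and no test is attached to them. As an endpoint name, responder appears in the SAP only for the CGI-I (section 5.3.1.10).

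**The concern.** Remission is normally read as a stricter state than response: few or no symptoms left, rather than a worthwhile reduction. Here it is the looser of the two. The protocol also disagrees with itself, because a 30% improvement is remission on the LSAS and response on the HDRS17. And the label sits badly with the entry rule in section 4.1 ("Subjects must have a Liebowitz Social Anxiety Scale score" of at least 70), since a subject who started high can be called remitted while still severe enough to enrol.

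At stake is how the result is described. If the protocol's name were carried into the study report, the share of subjects with partial improvement would appear as a remission rate and would always look at least as good as the response rate.

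**Working it through.** The plan states no figure to reproduce on this point. The check is whether the two definitions nest, how far the lower one can sit from recovery, and whether any planned output depends on the name.

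**Inputs.** Cut-offs of 50% and 30% (protocol 9.3.2; SAP 5.3.1.3 and 5.3.1.4). Baseline LSAS *b* of at least 70 (protocol 4.1). Maximum score 144 (SAP 5.2.1). Week-12 score *w* from 0 to 144.

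**Step 1: the rules.** Percentage change is 100 × (*w* − *b*)/*b*. A change of −50 or less means *w* ≤ 0.5*b*. A change of −30 or less means *w* ≤ 0.7*b*. Since 0.5*b* < 0.7*b*, every subject meeting the first rule meets the second.

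**Step 2: enumeration.** For each whole-number baseline from 70 to 144, the number of qualifying week-12 scores is the rounded-down cut-off plus one.
- ≥30%: the sum of (⌊0.7*b*⌋ + 1) is 5,659 pairs.
- ≥50%: the sum of (⌊0.5*b*⌋ + 1) is 4,069 pairs.
- Meeting 50% but not 30%: 0 pairs.
- Meeting 30% but not 50%: 5,659 − 4,069 = 1,590 pairs.

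These count possible score pairs, each weighted equally. They confirm the nesting and say nothing about how many subjects fall where.

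**Step 3: distance from recovery.** The highest score that counts as remitted is 0.7 × 70 = 49 at baseline 70, 0.7 × 100 = 70 at baseline 100, and 100 at baseline 144 (0.7 × 144 = 100.8, rounded down). Remission with a score still at or above 70 is therefore possible from baseline 100 upwards, in 718 of the 5,659 pairs. The 50% rule has the same property in a much smaller corner: 0.5 × 140 = 70, so it begins at baseline 140 and covers 9 pairs.

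**Step 4: illustration of the gap.** Neither document gives a baseline mean, a baseline SD or an expected mean change. Assume a baseline mean of 95 and SD of 15, a mean change of −20 to −30 independent of baseline, and the change SD of 24 from protocol 11.2. Simulation then puts ≥50% improvement at 13.1% to 23.6% and ≥30% improvement at 35.8% to 51.8%. Between 1 − 23.6/51.8 = 54% and 1 − 13.1/35.8 = 63% of those called remitters would not be responders. These figures move with the assumptions, and the conclusion does not use them.

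**Step 5: what depends on the name.** The protocol attaches the word remission to a 30% rule. The SAP programs the same 30% rule under a neutral name. The variable, its denominator, its visits and its summary are the same under either name. The primary MMRM comparison, the one-sided 0.20 level and the sample size do not use it.

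**The case for a change.** The best case for a change is that the SAP never says it has renamed or dropped the protocol's remission endpoint. Someone matching protocol endpoints to SAP tables could head the ≥30% table remission, because section 9.3.2 says so and section 11.3 and the synopsis promise such a table. Three wording edits would close that off, with no new data or programming.

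The inversion, the mismatch with the HDRS17 wording and the reporting risk all stand. Three things weaken the case for action. First, protocol section 11 leaves the specific details of the analysis to the SAP, and the SAP's labels are clear, so outputs built from it carry no remission label. Second, section 9.3.2 prints the rule beside the name ("remitters (≥30% improvement from baseline"), so a reader of the definition is not misled about what is counted. Third, under section 17.1 even a wording edit needs a formal amendment, which is a lot of process for a change that moves no number.

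Nor is it certain which edit would be right. The cut-offs may have been swapped, 30% may have been meant as a second response level, or an absolute-score remission may have been intended. The SAP's two percentage variables and the HDRS17 wording favour the second reading. In the third case relabelling would not be enough, because the SAP has no such variable. Nothing in either document points to that case.

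**Conclusion.** The protocol's term is ill-chosen and, read literally, makes remission easier to reach than response. It is a clerical slip. The SAP already defines and tabulates both cut-offs under names that describe them, by counts and percentages only, so correcting the protocol would gain nothing in the planned analysis. The effect on every derivation, table, estimate, error rate and sample size is zero.

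This rests on two assumptions: that the two percentage cut-offs are what the sponsor means to report, and that the report keeps the SAP's labels rather than presenting the ≥30% rate as remission. An analyst working from the SAP would do the latter without further instruction.

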#### Exploratory

- The change from baseline to the 12-week endpoint for: SDS (Sheehan Disability Scale) GAD-7, Snaith-Hamilton Pleasure Scale (SHAPS) and MOS Sleep-R.
- The change from baseline to the 12-week endpoint for Quality of Life Enjoyment and Satisfaction Questionnaire (Q-LES-Q)
- Self-Assessment of Treatment Experience scale
- The change from baseline to the 12-week endpoint for: HDRS17 total score, HDRS17 anxiety/somatization factor total score and HAM-D6 score in subjects with comorbid MDD.
- The change from baseline to the 12-week endpoint for: SIGH-A total score and HAM-A6 score in subjects with comorbid GAD.
- The distribution (number and percentage) of subjects with comorbid MDD who are responders on depressive symptoms (based on two definitions: either  $\geq$ 50% or  $\geq$ 30% improvement on HDRS17 total score from baseline) at the 12-week endpoint.
- The distribution (number and percentage) of subjects with comorbid GAD who are responders on anxious symptoms (≥50% improvement on SIGH-A total score from baseline) at the 12-week endpoint.

